Appendix 2. C-SSRS Mapped to C-CASA - Suicidal Ideation and Behavior Events and Codes

C-CASA Event Code	C-CASA Event	C-SSRS Response
1	Completed suicide	As captured in the safety database
2	Suicide attempt	“Yes” on “Actual Attempt”
3	Preparatory acts towards imminent suicidal behavior	“Yes” on any of the following: 
 • “Aborted attempt”, or • “Interrupted attempt”, or • “Preparatory Acts or Behavior”
4	Suicidal ideation	“Yes” on any of the following: 
 • “Wish to be dead”, or • “Non-Specific Active Suicidal Thoughts”, or • “Active Suicidal Ideation with Any Methods (Not Plan) without Intent to Act”, or • “Active Suicidal Ideation with Some Intent to Act, without Specific Plan”, or • “Active Suicidal Ideation with Specific Plan and Intent”
7	Self-injurious behavior, no suicidal intent	“Yes” on “Has subject engaged in Non-suicidal Self-Injurious Behavior?”

Appendix 3. Windowing for Study Months 1, 2 and 3

A 28-day seizure rate will be determined for each windowed month for which seizure data exist. Assignment of seizure data to visits during the Double-Blind Treatment Phase will use visit windows based on the day of the assessment relative to the date of the start of the double blind treatment phase. The following visit windows will be defined for statistical outputs:

Visit Windows

Month	Time Interval (Days)
Month 1	1 to 28
Month 2	29 to 56
Month 3	57 to 90

Derive study day as the (assessment date-date of start of double blind treatment phase) + 1. A subject must have at least 24 diary days to be counted in any monthly visit window data. Any data collected after Day 90 will be excluded from the monthly visit window calculations.

Appendix 4. Analysis Strategy Using Multiple Imputations

If the amount of missing data is not significant in the primary endpoint (ie, less than 5% within each treatment groups), then the multiple imputation analysis will not be performed.

Concept of multiple imputation strategy

Multiple imputation procedure is used under the assumption of missing at random (MAR) data and under the assumption of a monotone missing data pattern. In general, let \mathbf{Y} be the response data (monthly seizure rate) where that part of \mathbf{Y} which is missing is denoted by \mathbf{Y}_{mis} , and that part of \mathbf{Y} which is observed is denoted by \mathbf{Y}_{obs} . A data pattern is said to have a missing monotone data pattern when the variable \mathbf{Y}_j for an individual subject is missing at time point j , and all subsequent variables for that individual are also missing for \mathbf{Y}_k in which $k > j$.

The three steps for conducting statistical inferences using a multiple imputation procedure consist of the following:

Imputation step: Missing data are filled in m times to generate m complete data sets, where $m > 1$; For this study, we will let m take on the value 100.

Analysis step: The m complete data sets are analyzed using standard procedures;

Combination step: The results from the m complete data sets are combined for the final statistical inference.

The imputation step is perhaps the most critical, since it relies upon assumptions regarding the missing data mechanism. The goal of the imputation is to account for the relationships between the unobserved and observed variables, while taking into account the uncertainty of the imputation. The MAR assumption is key to the validity of multiple imputation. Use of this assumption allows the analyst to generate imputations $(\mathbf{Y}_{\{1\}}, \mathbf{Y}_{\{2\}}, \dots, \mathbf{Y}_{\{m\}})$ from the distribution $f(\mathbf{Y}_{\text{mis}} | \mathbf{Y}_{\text{obs}})$, since after conditioning on \mathbf{Y}_{obs} , the missingness is assumed to be due to chance and is considered ignorable. In this application, we will use the regression method in which the variable \mathbf{Y}_j with missing values, is fitted with non-missing observations as the dependent variables. This allows for the following regression model to be employed:

$$\mathbf{Y}_j = \beta_0 + \beta_1 * \mathbf{Y}_1 + \beta_2 * \mathbf{Y}_2 + \dots + \beta_{(j-1)} * \mathbf{Y}_{(j-1)}.$$

The fitted model has parameter estimates $(b_0, b_1, b_2, \dots, b_{(j-1)})$ and the associated covariance matrix $s_j^2 V_j$, where V_j is the usual $\mathbf{X}^T \mathbf{X}$ matrix from the intercept and variables $\mathbf{Y}_1, \mathbf{Y}_2, \dots, \mathbf{Y}_{(j-1)}$.

For each imputation, new parameters ($\beta_0^*, \beta_1^*, \beta_2^*, \dots, \beta_{(j-1)}^*$; and σ^{*2}) are drawn from a posterior predictive distribution of the missing data. The missing values of Y_j are then replaced with the predicted values using the following equation:

$$\beta_0^* + \beta_1^* * y_1 + \beta_2^* * y_2 + \dots + \beta_{(j-1)}^* * y_{(j-1)} + z_i * \sigma^{*2}$$

where $y_1, y_2, \dots, y_{(j-1)}$ are covariates values for the first $(j-1)$ variables and z_i a simulated standard normal deviate for the i^{th} individual.

The next step is to carry out the analysis of interest for each of the m imputed complete-observation datasets, storing the parameter vector and standard error estimates.

Finally, the results are combined using results from Rubin (1987), to calculate estimates of the within imputation and between imputation variability. These statistics account for the variability of the imputations and assuming that the imputation model is correct, provide consistent estimates of the parameters and their standard errors.

SAS sample programs for multiple imputation strategy for this study

A pattern mixture model of multiple imputation is applied, and sample SAS programs are described as below. Note that the variable names/labels are suggestions only and the actual names/labels and code levels should be consistent with current sponsor reporting standards.

- SUBJID: subject identification number.
- REGION and AGE_strata (See covariates [Section 6.4](#)).
- TRT: Treatment group (Placebo, Pregabalin Level 1, Pregabalin Level 2).
- LN_BSZRT: A \log_e transformed baseline seizure rate $\log_e(28\text{-days seizure rate}_t + 1)$.
- LN_SZRATE: A \log_e transformed double-blind seizure rate $\log_e(28\text{-days seizure rate}_t + 1)$.
- IMPSTAT: Impstat = 1 if DC due to AE, death, or insufficient clinical response. Impstat = 2 otherwise.
- MISS: Miss = 1 if ln_szrate is missing. Miss = 0 otherwise.

In order to impute missing data at the singular time point, first prepare an input dataset, making sure that it will contain only the intended donor and recipient patterns. Separate the input dataset <efficacy> into two datasets: IMP, containing all placebo subjects and those subjects from the pregabalin arms that have missing LN_SZRATE [Miss=1] and

Impstat=1; and REST, containing the rest of the subjects from the pregabalin arms (those with non-missing LN_SZRATE [Miss=0] or Impstat=2).

title1 'Pattern Imputation based on reason for DC';

```
*these sets are exhaustive and mutually exclusive;
data IMP REST;
  set <efficacy>;
  if trt ne "Placebo" and (impstat = 2 or miss = 0) then output REST;
  else output IMP;
run;
```

Call PROC MI to impute missing data at the time point using dataset IMP as input.

*order of variables matters in proc mi;

```
proc mi data = IMP out = impout n impute=100 seed = 100;
  class region age_strata;
  var region age_strata ln_bszrt ln_szrate weight;
  monotone regression(ln_szrate = ln_bszrt region age_strata weight);
run;
```

Call PROC MI to impute missing data at the time point using dataset REST as input.

*impute like randomized trt for active who are 'ignorably missing';

```
proc mi data = REST out = restout n impute=100 seed = 101 ;
  class region age_strata trt ;
  var region age_strata trt ln_bszrt ln_szrate weight;
  monotone regression(ln_szrate = trt ln_bszrt region age_strata weight) ;
run;
```

Assemble back a dataset containing all subjects.

*fully imputed integrated dataset;

```
data main ;
  set impout restout ;
run ;
proc sort data = main ;
  by _imputation_ trt ;
run ;
```

*Analysis of imputed data sets;

* Confirm the ordering of the trt variable for specifying the vector. Here it is assumed Placebo, Pregabalin Level 1, and Pregabalin Level 2 ;

```
proc glm data=main;
  by _imputation_ ;
  class region age_strata trt ;
  model ln_szrate = trt region age_strata ln_bszrt;
```

```
lsmeans trt / diff=control('Placebo') tdiff pdiff cl ;
estimate 'Pregabalin Level 1 vs Placebo' trt -1 1 0 ;
estimate 'Pregabalin Level 2 vs Placebo' trt -1 0 1 ;
ods output lsmeans=lsm diffs=lsdiff estimates=estdiffs ;
run ;
quit ;
```

```
*integrated summary of results of imputed datasets;
proc mianalyze parms(classvar=full)=lsm edf=xxx;
  class trt ;
  modeleffects trt ;
run ;
proc sort data = estdiffs ;
  by parameter _imputation_ ;
run ;
proc mianalyze data=estdiffs ;
  by parameter ;
  modeleffects estimate ;
  stderr stderr ;
run ;
```

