7. HANDLING OF MISSING VALUES

Missing data will be handled based on the nature of the endpoint and the proposed statistical methods for analyzing the data.

For all endpoints that include seizure rate, days with missing seizure diary data will be subtracted from the seizure rate calculations. If seizure rate for any phase cannot be calculated for a subject due to missing information, the endpoint that involves seizure rate during that phase will be also missing for that subject.

For scales used in this study, scores will be imputed according to the imputation rules and algorithms for missing component scores that are provided in the data standard documents. Partial dates for AEs and concomitant medications will be imputed according to Pfizer standard algorithms.

The assessment of missing data for the primary endpoint will require the construction of the following windows and drop-out categories:

- *Windowing for each subject will be constructed for the 1st month, 2nd month, and 3rd month the subject was in the study. Thus a 28-day seizure rate will be determined for each windowed month for which seizure data exist, otherwise the seizure data will be considered missing with a corresponding reason for it being missing. Specific details are provided in [Appendix 3](#).*
- *Drop-out patterns will be constructed based on the reason the seizure data is missing for the corresponding windowed month. Hence, the following drop-out patterns will be defined for three specific categories of related to lack of efficacy or adverse event or other reason:*
 - *Completed study as planned.*
 - *Drop-out due to lack of efficacy:*
 - *Drop-out at month 1 due to lack of efficacy;*
 - *Drop-out at month 2 due lack of efficacy;*
 - *Drop-out at month 3 due to lack of efficacy.*
 - *Drop-out due to an adverse event:*
 - *Drop-out at month 1 due to an adverse event;*
 - *Drop-out at month 2 due to an adverse event;*
 - *Drop-out at month 3 due to an adverse event.*
 - *Drop-out due to other reason:*
 - *Drop-out at month 1 due to other reason;*
 - *Drop-out at month 2 due to other reason;*
 - *Drop-out at month 3 due to other reason.*

Other reason includes any drop-outs excluding efficacy and adverse event.

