Other analyses of continuous dependent variables with ANCOVA model will follow the same procedure as the primary efficacy endpoint analysis. Responder rates and any other binary variables that use the same planned model as primary efficacy endpoint analysis will similarly be adjusted as needed.

Sensitivity Analysis

As a sensitivity analysis of the primary endpoint, multiple imputation methods will be used to evaluate the impact of missing data (See [Appendix 4](#)).

Subjects who discontinue the study for insufficient clinical response, adverse event, or death will be imputed based on the observed placebo distribution, regardless of randomized treatment assignment. Imputation will be based on baseline $\log_e(28\text{-days seizure rate}_b + 1)$, geographical region, baseline weight (continuous), and age strata.

Subjects who discontinue the study for other reasons, or who complete the study but have a missing double blind seizure rate, will be imputed based on observed subjects in the same randomized treatment group. Imputation will be based on treatment group, baseline $\log_e(28\text{-days seizure rate}_b + 1)$, geographical region, baseline weight (continuous), and age strata.

A sensitivity analysis will be performed using the same linear model as the primary efficacy analysis except for the age covariate, which will be applied for the 2 age groups (5-16 years of age; 17-65 years of age).

An additional sensitivity analysis will be performed using the same linear model as the primary efficacy analysis with two age groups covariate as well as pooled region of US and European Union.

A ranked ANCOVA will be performed for the change from baseline to double blind phase of log-transformed (\log_e) 28-day seizure rate for all PGTC seizures, including age strata, treatment group, and region.

A Wilcoxon-Mann Whitney test will also be performed and reported for the change from baseline to double blind phase of log-transformed (\log_e) 28-day seizure rate for all PGTC seizures.

Supplemental Analysis

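### The multiple-imputation sensitivity analysis in SAP Appendix 4 would impute almost no drop-outs, because nearly every ITT drop-out has a calculable double-blind seizure rate

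*SAP*

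**What the plan says.** **Who is to be imputed, SAP Section 8.1.** "Subjects who discontinue the study for insufficient clinical response, adverse event, or death will be imputed based on the observed placebo distribution", whatever their arm. A second rule covers those who stop for other reasons and those "who complete the study but have a missing double blind seizure rate"; they are imputed from their own arm. The condition of a missing rate is attached to completers only.

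**Who is imputed, SAP Appendix 4.** The flag is "MISS: Miss = 1 if ln_szrate is missing. Miss = 0 otherwise", where LN_SZRATE is the single log rate for the whole double-blind phase. The dataset IMP holds all placebo subjects and "those subjects from the pregabalin arms that have missing LN_SZRATE [Miss=1" together with a stop for adverse event, death or lack of response. In the code, pregabalin subjects are sent the other way by "impstat = 2 or miss = 0) then output REST".

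**When a rate is missing.** Section 7 gives one rule: "If seizure rate for any phase cannot be calculated for a subject due to missing information", the endpoint is missing too. Section 6.1.1 and Appendix 1 compute the rate from first to last dose in the phase, less missing diary days. The 24-day minimum in Appendix 3 applies to monthly windows only. Section 5.1 admits a subject to ITT only with a baseline value and a diary entry after baseline.

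**The threshold.** Section 7 omits imputation if less than 5% is missing, taken over all treatment groups. Appendix 4 omits it if less than 5% of the primary endpoint is missing in each group.

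**The concern.** A drop-out who kept a diary for even one day on treatment has a rate under the SAP's formula. The flag is then 0 and nothing is imputed. The design that sends subjects to a placebo or own-arm model by reason for stopping would have almost no one to act on.

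The Section 8.5 table lists 12 efficacy analyses. Eight handle missing data by subtracting missing diary days, three leave the cell blank, and this one alone imputes. Section 8.1 presents it as the evaluation of the impact of missing data. If it hardly differs from the primary analysis by construction, agreement between the two could be taken for robustness to drop-out when it shows nothing of the kind.

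**Working it through.** **1. The plan's own figure.** Section 2.2 gives power 0.800 for a difference of 0.358, SD 0.67, 56 per group, two-sided 0.05. The noncentrality is 0.358 / (0.67 × √(2/56)) = 2.83. The two-sample t calculation gives 0.800 and the normal approximation 0.807. The figure reproduces, so 56 per arm is used below.

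**2. When an ITT drop-out lacks a rate.** With S seizures, D days from first to last dose and m missing diary days, the rate is 28 × S / (D − m). It exists whenever m < D. For the drop-out at day 26 used as the example in Appendix 5, it is 28 × S / (26 − m), defined with a single diary day. Apart from missing dose dates, an ITT subject lacks a rate only if every diary entry after baseline falls outside the interval from first to last dose.

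Before the ITT rule is applied, a simulation with assumed inputs (drop-out 10% to 30%, last dose uniform over days 1 to 83, 5% to 50% of diary days missing at random) left 0.06% to 1.2% of treated drop-outs without a rate. That is 0.006% to 0.37% of all treated subjects. In this set-up ITT entry removes all of them.

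**3. The two texts side by side.**

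| Subject | Section 8.1, literal | Appendix 4 |
|---|---|---|
| Pregabalin, stopped for adverse event or lack of response, or died; has partial rate | imputed from placebo | in REST, keeps rate, donor |
| Pregabalin, stopped for other reason, has partial rate | imputed from own arm | in REST, keeps rate, donor |
| Placebo, stopped for any reason, has partial rate | imputed from placebo | in IMP, keeps rate, donor |
| Completer without a rate | imputed from own arm | imputed |

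The texts differ in the first three rows, which are the drop-outs the analysis is about.

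**4. The 5% threshold.** The smallest counts reaching 5% are 3/56 = 5.4% (2/56 = 3.6%), or 9/168 = 5.4% pooled (8/168 = 4.8%). At the cap of 65 per arm the count is 4/65 = 6.2%. With independent subjects, each counted with probability q, the chance that at least one of three arms reaches 3 of 56 is 1 − (1 − P[X ≥ 3])³. For q = 1%, P[X ≥ 3] = 1 − (0.5696 + 0.3222 + 0.0895) = 0.0187, and 1 − 0.9813³ = 0.055.

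| What is counted (q assumed) | Any arm ≥ 3 of 56 | Pooled ≥ 9 of 168 |
|---|---|---|
| No calculable rate, 0.5% | 0.9% | under 0.01% |
| No calculable rate, 1% | 5.5% | under 0.01% |
| No calculable rate, 2% | 27.5% | 0.7% |
| Discontinuers, 10% | above 99.9% | 98.9% |
| Discontinuers, 15% or 20% | above 99.9% | above 99.9% |

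At 4 of 65 per arm, the first three per-arm figures become 0.1%, 1.3% and 11.9%.

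**5. Variable order.** Appendix 4 describes regressing each variable on those before it, and a comment in its code says that order matters. Yet the first program has "var region age_strata ln_bszrt ln_szrate weight" and the second likewise puts weight last, although weight is a predictor of the outcome in both models.

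**The case against.** **Section 8.1 may mean missing values only.** Its opening speaks of the impact of missing data and points to Appendix 4 for detail. This is a fair reading, so a reader who infers a flat contradiction goes further than the text allows. On this reading the two places agree, but step 2 still leaves the analysis nearly empty.

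**The programs are samples.** Appendix 4 also tells the analyst to prepare the input first, "making sure that it will contain only the intended donor and recipient patterns". Drop-outs' rates could be set to missing at that step. But no rule says so, and the label of suggestion is given to variable names and labels. The prose describing IMP also requires a missing rate, so the restriction is not only in the code.

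**The threshold may count drop-outs.** A reader might infer that it would probably cancel the analysis. The documents do not establish that. Section 7 introduces the monthly windows and drop-out patterns as the assessment of missing data for the primary endpoint and states the threshold right after them, and the concept text of Appendix 4 treats the response as a monthly rate. If discontinuers are counted, the analysis would almost surely run at 10% drop-out or more. It would still impute almost nobody.

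**Other analyses bear on drop-out.** The Poisson and negative binomial models offset exposure time, drop-out patterns are tabulated by arm, and Appendix 1 counts subjects with no double-blind rate as non-responders. These are useful, but none replaces imputation by reason for stopping.

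**The primary endpoint uses observed days on purpose.** That stands, and it is why the change should be confined to this sensitivity analysis.

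**Conclusion.** The point holds and should be fixed before unblinding. Followed as written, Appendix 4 imputes almost no ITT drop-out, and the analysis would nearly repeat the primary result whether or not the threshold is met. This follows from the definitions of the rate, the flag and the ITT set, and needs no assumed drop-out rate.

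Whether the analysis would run at all is undetermined: from 0.9% to above 99.9% by arm, depending on what is counted. The documents give no rate of drop-out or of missing endpoints, so every q above is an assumption.

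A reader might also infer that the primary result is biased in a known direction. The documents do not support that: neither the size nor the direction of any change in the treatment difference can be derived from them. The primary test, type I error and sample size are unaffected. The statement that no rule sets a drop-out's rate to missing is made about the SAP text.

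**What to change.** While the study is blinded, reconcile Sections 7 and 8.1 with Appendix 4:

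1. For this sensitivity analysis only, set LN_SZRATE to missing in the input dataset for subjects in any arm who discontinue the double-blind phase. The existing split then sends pregabalin stops for adverse event, death or lack of response to IMP, keeps other pregabalin stops in REST, makes placebo drop-outs recipients, and leaves as donors those who completed with a rate.
2. Keep the condition on the flag being 0 in the split. It keeps observed pregabalin rates out of the placebo donor model.
3. State one 5% threshold, in the same words in both places, counting discontinuers plus completers without a rate. Or drop the threshold.
4. List weight before ln_szrate in both VAR statements.

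The cost is SAP wording and a small change to one input dataset; no new data are needed. The downside is that drop-outs' partial data go unused in this one analysis, and its estimate may move either way from the primary one. If the sponsor prefers to keep observed days, imputing only the missing months is an alternative, closer to the monthly response in the Appendix 4 concept text, but it would need its own specification.

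### Appendix 4's sample imputation code lists weight after the outcome it must predict, and gives no complete-data degrees of freedom when pooling the treatment differences

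*SAP*

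**What the plan says.** Section 8.1 of the SAP (Sensitivity Analysis) describes the imputation in words. Subjects who stop for insufficient response, an adverse event or death are imputed from the placebo distribution; other missing outcomes are imputed from the subject's own randomized group. In both cases the predictors include "geographical region, baseline weight (continuous), and age strata" together with the baseline log rate, and treatment group is added for the own-group imputations. No variable order is given there.

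Appendix 4 assumes a monotone pattern: once a variable is missing for a subject, "all subsequent variables for that individual are also missing". Variable j is regressed on variables 1 to j-1. The sample program comments that "order of variables matters in proc mi". Its two VAR lists read "var region age_strata ln_bszrt ln_szrate weight" and "var region age_strata trt ln_bszrt ln_szrate weight". The first imputation model is "monotone regression(ln_szrate = ln_bszrt region age_strata weight", closing bracket omitted here; the second adds treatment.

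For pooling, the PROC MIANALYZE call on the LS means has an EDF option with a placeholder value. The call on the treatment differences, "proc mianalyze data=estdiffs", has none.

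In the variable list of the same appendix, LN_BSZRT is described as the "transformed baseline seizure rate" on the log scale, but its formula carries the treatment-phase subscript t.

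**The concern.** A subject who needs imputation and has a recorded baseline weight shows, in the printed order, a missing value followed by an observed one. That is not the monotone pattern the appendix assumes. Weight is also the one predictor that the appendix's own regression rule does not admit at that position, yet Section 8.1 pre-specifies it.

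The second issue is the reference distribution for the pooled differences. These are the comparisons of interest, and they are pooled without the complete-data degrees of freedom that the neighbouring call supplies for the arm means. The intervals then rest on far more degrees of freedom than the ANCOVA has.

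At stake is whether the imputation-based check on the primary result can be programmed as printed, and whether its intervals are exact. Neither issue reaches the primary test.

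**Working it through.** **Sample size behind the degrees of freedom.** SAP Section 2.2 gives 56 per group, a difference of 0.358, an SD of 0.67, two-sided alpha 0.05 and power 0.800. The standardized difference is 0.358 / (0.67 × √(2/56)) = 0.358 / 0.1266 = 2.827. The normal approximation gives power Φ(2.827 − 1.960) = 0.807, and the noncentral t with 110 df gives 0.800. The plan's figure is reproduced. It serves only to confirm N = 168; no stated number is disputed.

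**Variable order.** Position of each variable in the VAR lists:

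| Call | Before the outcome | Outcome | After the outcome |
|---|---|---|---|
| First, as printed | region 1, age_strata 2, ln_bszrt 3 | ln_szrate 4 | weight 5 |
| Second, as printed | region 1, age_strata 2, trt 3, ln_bszrt 4 | ln_szrate 5 | weight 6 |
| First, reordered | region 1, age_strata 2, weight 3, ln_bszrt 4 | ln_szrate 5 | none |
| Second, reordered | region 1, age_strata 2, trt 3, weight 4, ln_bszrt 5 | ln_szrate 6 | none |

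As printed, the pattern with ln_szrate missing and weight observed is not monotone in either call, and weight is the only predictor that does not precede the outcome. Reordered, the pattern is monotone in both calls and every predictor precedes the outcome, provided the baseline covariates are complete.

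The method itself is feasible. Section 8.1 coded directly, outside SAS, on one simulated data set of 168 subjects with about 10% missing outcomes ran through and gave 158 residual df.

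**Degrees of freedom.** Inputs:
- m = 100 imputations (Appendix 4).
- Analysis-model parameters: 1 intercept + 2 treatment + 3 region + 3 age strata + 1 baseline = 10.
- Complete-data df ν₀ = 168 − 10 = 158, or 195 − 10 = 185 at the maximum sample size.
- λ, the share of the pooled variance due to missing data, is an assumption: 0.01 to 0.30.
- Omitting EDF is taken to mean that the complete-data df are treated as infinite.

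Formulas:
- Without EDF (Rubin): ν = (m − 1)/λ².
- With EDF (small-sample form): ν_obs = [(ν₀ + 1)/(ν₀ + 3)] × ν₀ × (1 − λ), and 1/ν* = 1/ν + 1/ν_obs.

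Example at N = 168, λ = 0.10: ν = 99/0.01 = 9,900; ν_obs = (159/161) × 158 × 0.90 = 140.4; ν* = 138.5.

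| N | λ | df without EDF | df with EDF | t without | t with | Interval too narrow by | Actual alpha |
|---|---|---|---|---|---|---|---|
| 168 | 0.01 | 990,000 | 154.5 | 1.960 | 1.975 | 0.79% | 0.0518 |
| 168 | 0.05 | 39,600 | 147.7 | 1.960 | 1.976 | 0.82% | 0.0519 |
| 168 | 0.10 | 9,900 | 138.5 | 1.960 | 1.977 | 0.87% | 0.0520 |
| 168 | 0.20 | 2,475 | 118.8 | 1.961 | 1.980 | 0.98% | 0.0522 |
| 168 | 0.30 | 1,100 | 99.4 | 1.962 | 1.984 | 1.12% | 0.0525 |
| 195 | 0.01 | 990,000 | 181.2 | 1.960 | 1.973 | 0.67% | 0.0515 |
| 195 | 0.30 | 1,100 | 114.8 | 1.962 | 1.981 | 0.95% | 0.0522 |

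The narrowing is the ratio of the two critical values minus 1. At every λ examined, the df without EDF exceed what the ANCOVA would have with no data missing.

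**Subscript.** LN_BSZRT and LN_SZRATE carry the same formula in Appendix 4. Sections 6.4 and 8.1 write the baseline covariate with subscript b.

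**The case against.** The strongest reply is that Section 8.1 already fixes the donors and the predictors, and that Appendix 4 calls its programs samples. A competent programmer would move one word per list and keep weight, with no analytic choice left open. This largely stands: the method is sound and the repair is obvious. It does not clear the printed code, because the appendix's caveat covers variable names, labels and code levels, not variable order, and the program itself warns that order matters.

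It can also be said that the monotone definition is written for monthly seizure rates, so applying it to weight extends the text. That is fair. The program, however, applies the same regression method to its VAR list, and the rule of using only earlier variables then governs weight too.

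On EDF, Appendix 4 says results are combined following Rubin (1987), and the classical formula is what results when EDF is left out. The effect is about 1% of interval width in an analysis outside the testing sequence. The small size stands. The inconsistency between two adjacent calls also stands.

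Few subjects may be involved. The ITT set requires at least one post-baseline diary entry, and the rate uses whatever diary days exist, so many who leave early will still have an outcome. The imputation is skipped below 5% missing (Section 7 and Appendix 4).

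**Conclusion.** The point holds as a minor coding defect in two parts. Both sample PROC MI calls list weight after the outcome it is specified to predict, contrary to Appendix 4's own set-up. The pooled treatment differences lack the complete-data df, which makes their intervals about 0.8% to 1.1% too narrow at N = 168 (0.7% to 1.0% at N = 195) and puts a nominal 0.05 test at about 0.052. The size rests on the assumed λ range, a 10-parameter model and omitted EDF meaning infinite complete-data df.

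Four stronger readings are tempting, and the documents do not support them:

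- A reader might infer that the Section 8.1 imputation cannot run, or that weight must be dropped. The fault lies in the sample code only, reordering keeps weight, and whether SAS would stop is neither stated nor tested.
- A reader might infer that the plan's only assessment of missing data fails. Section 7 also plans drop-out summaries by arm and refers to Appendix 5, a count model with an exposure offset.
- A reader might infer that the treatment-phase rate would be used as the baseline covariate. The description says baseline, and Sections 6.4 and 8.1 use subscript b, so the slip is clerical.
- A reader might infer that the primary conclusion is at risk. The primary ANCOVA uses neither the imputation nor the pooling.

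**What to change.** In Appendix 4:

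1. Change the first list to `var region age_strata weight ln_bszrt ln_szrate` and the second to `var region age_strata trt weight ln_bszrt ln_szrate`.
2. Give the ANCOVA error df as EDF in both PROC MIANALYZE calls, replacing the placeholder in one and adding the option to the other: 158 at 168 subjects with 10 parameters, recalculated for the final N and model.
3. Change the LN_BSZRT subscript from t to b.

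The cost is a few edits to sample code, best made before unblinding. No data collection, sample size, predictor or test changes.
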